5.2.3 Adverse Events of Special Interest (Immediately Reportable to the Sponsor)

Adverse events of special interest are required to be reported by the investigator to the Sponsor immediately (i.e., no more than 24 hours after learning of the event; see Section 5.4.2 for reporting instructions). Adverse events of special interest for this study are as follows:

- Cases of potential drug-induced liver injury that include an elevated ALT or AST in combination with either an elevated bilirubin or clinical jaundice, as defined by Hy's Law (see Section 5.3.5.7)
- Suspected transmission of an infectious agent by the study drug, as defined below
 - Any organism, virus, or infectious particle (e.g., prion protein transmitting transmissible spongiform encephalopathy), pathogenic or non-pathogenic, is considered an infectious agent. A transmission of an infectious agent may be suspected from clinical symptoms or laboratory findings that indicate an infection in a patient exposed to a medicinal product. This term applies only when a contamination of the study drug is suspected.
- Grade ≥ 3 hepatitis or elevations in AST or ALT
- Grade ≥ 3 acute kidney injury, creatinine increase, or renal toxicity
- Grade ≥ 2 bradycardia
- Grade ≥ 2 thromboembolism

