5.3.5.2 Diagnosis versus Signs and Symptoms

A diagnosis (if known) should be recorded on the Adverse Event eCRF rather than individual signs and symptoms (e.g., record only liver failure or hepatitis rather than jaundice, asterixis, and elevated transaminases). However, if a constellation of signs and/or symptoms cannot be medically characterized as a single diagnosis or syndrome at the time of reporting, each individual event

should be recorded on the Adverse Event eCRF. If a diagnosis is subsequently established, all previously reported adverse events based on signs and symptoms should be nullified and replaced by one adverse event report based on the single diagnosis, with a starting date that corresponds to the starting date of the first symptom of the eventual diagnosis.

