5.3.5.7 Abnormal Liver Function Tests

The finding of an elevated ALT or AST ($>3\times$ baseline value) in combination with either an elevated total bilirubin ($>2\times$ ULN) or clinical jaundice in the absence of cholestasis or other causes of hyperbilirubinemia is considered to be an indicator of severe liver injury (as defined by Hy's Law). Therefore, investigators must report as an adverse event the occurrence of either of the following:

- Treatment-emergent ALT or AST $>3\times$ baseline value in combination with total bilirubin $>2\times$ ULN (of which $\geq 35\%$ is direct bilirubin)
- Treatment-emergent ALT or AST $>3\times$ baseline value in combination with clinical jaundice

The most appropriate diagnosis or (if a diagnosis cannot be established) the abnormal laboratory values should be recorded on the Adverse Event eCRF (see Section 5.3.5.2) and reported to the Sponsor immediately (i.e., no more than 24 hours after learning of the event), either as a serious adverse event or an adverse event of special interest (see Section 5.4.2).

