5.6.2 Adverse Events

Adverse events will be mapped to MedDRA thesaurus terms and appropriate MedDRA hierarchy. Adverse event severity will be graded according to NCI CTCAE v5.0. Multiple occurrences of the same event will be counted once at the maximum severity.

The frequency, nature, and severity of treatment-emergent adverse events, adverse events leading to death, adverse events leading to study drug discontinuation, serious adverse events, and adverse events of special interest will be summarized by treatment arm. All deaths will be summarized. Treatment-emergent adverse events are defined as adverse events that occur after the first dose of study treatment.

Relevant vital signs will be presented using summary statistics by treatment received. Selected laboratory and vital sign data will be summarized by treatment received, and

grade compared with baseline and measurements outside of the normal range will be identified.

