5.6.3 Laboratory Data

Relevant laboratory values will be summarized by treatment arm over time, with NCI CTCAE v5.0 Grade 3 and Grade 4 values identified, where appropriate. Summary tables of clinically relevant shifts in NCI CTCAE v5.0 grades (Grades 1, 2) at baseline to the worst post-baseline (Grade ≥ 3) value will be presented.

A Hy's Law analysis will be provided: the finding of an elevated ALT or AST ($> 3x$ upper limit of normal [ULN]) in combination with either an elevated total bilirubin ($> 2x$ ULN) or clinical jaundice in the absence of cholestasis or other causes of hyperbilirubinemia is considered to be an indicator of severe liver injury (as defined by Hy's Law).

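### SAP 5.6.3 and Protocol 5.3.5.7 give Hy's Law different transaminase references (3x ULN versus 3x baseline) without explanation; as a lesser point, the described SAP shift table has no normal-baseline row

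*SAP*

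**What the plan says.** SAP 5.6.3 plans a Hy's Law analysis. Its transaminase limb is ALT or AST more than three times the "upper limit of normal [ULN]) in combination with either an elevated total bilirubin" (above 2x ULN) or clinical jaundice, with cholestasis and other explanations for the bilirubin excluded.

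Protocol 5.3.5.7 has a matching definition sentence under the same name, except that the transaminase limb is more than three times the patient's "baseline value) in combination with either an elevated total bilirubin" or jaundice. It then says that "investigators must report as an adverse event the occurrence of either of the following". The two reporting bullets that follow require a treatment-emergent elevation and, for the bilirubin limb, at least 35% direct bilirubin. They do not repeat the exclusion of other causes.

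Two other parts of the protocol rely on 5.3.5.7. The special-interest event list in 5.2.3 includes "Cases of potential drug-induced liver injury that include an elevated ALT or AST in combination with either an elevated bilirubin or clinical jaundice", with a reference to that section. Table 1 in 5.1.3.3 ties one of its actions to meeting the same definition. SAP 5.6.2 states that "serious adverse events, and adverse events of special interest will be summarized by treatment arm".

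On laboratory shifts, SAP 5.6.3 describes tables running from Grade 1 or 2 at baseline to a worst post-baseline Grade 3 or higher.

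**The concern.** Hepatotoxicity is an identified risk of the test drug (Protocol 5.1.1.6). The one planned output called Hy's Law uses a different transaminase reference from the protocol definition of that name, and a reader of the output would not be told. The analysis and the site-reported cases can therefore identify different patients. A fixed multiple of ULN can also be met by an elevation that was present before the first dose, because Protocol 4.1.1 admits patients with liver metastasis up to 5x ULN.

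The clause in SAP section 5 that gives the SAP precedence does not settle this. It covers analyses, whereas Protocol 5.3.5.7 governs what sites report.

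The shift table raises a separate and smaller question. A patient who goes from normal to Grade 3 or higher has no row in the table as described.

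**Working it through.** There is no stated figure to reproduce, so the check compares the two rules.

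**Inputs.** SAP transaminase limb: peak above 3x ULN (SAP 5.6.3). Protocol transaminase limb: peak above 3x baseline (Protocol 5.3.5.7). Entry limits from Protocol 4.1.1: ALT and AST up to 3x ULN, or 5x with liver metastasis; bilirubin up to 1.5x ULN, or 3x with known Gilbert syndrome. The individual baselines below are illustrative assumptions inside those limits.

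**Formula.** Let b be baseline and p the peak, both in multiples of ULN. The protocol limb is p > 3b and the SAP limb is p > 3. They disagree when p is above min(3b, 3) and no higher than max(3b, 3). The disagreement is protocol-only if b < 1 and SAP-only if b > 1. The fold change from baseline needed to pass the SAP limb is 3/b.

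| Baseline b | Protocol threshold 3b | Peaks where the limbs disagree | Met by | SAP fold change 3/b |
|---|---|---|---|---|
| 0.5 | 1.5 | >1.5 to 3 | protocol only | 6.0 |
| 0.75 | 2.25 | >2.25 to 3 | protocol only | 4.0 |
| 1 | 3 | none | – | 3.0 |
| 2 | 6 | >3 to 6 | SAP only | 1.5 |
| 3 (limit without liver metastasis) | 9 | >3 to 9 | SAP only | 1.0 |
| 4 | 12 | >3 to 12 | SAP only | 0.75 |
| 5 (limit with liver metastasis) | 15 | >3 to 15 | SAP only | 0.6 |

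The disagreement runs in both directions and is not confined to patients with liver metastasis. A fold change below 1 means that the SAP limb is already met at baseline. At b = 4 an unchanged post-dose value of 4x ULN still exceeds 3x, so restricting the analysis to post-dose values does not remove that patient. Only a baseline flag identifies the case.

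**Bilirubin.** These windows are thresholds, not case counts. A patient without Gilbert syndrome at the entry cap of 1.5x ULN passes 2x ULN after a rise of more than 2.0/1.5 = 1.33-fold. Gilbert syndrome allows a higher entry value but is itself another explanation for raised bilirubin, so the SAP's exclusion would apply.

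**Shift table.** Of the baseline grades from which a patient can worsen to Grade 3 or higher, the description lists 1 and 2 and leaves out 0.

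**The case against.** The strongest reply is that nothing competes. Protocol 6.5.1 specifies no Hy's Law analysis, the SAP states its own definition in full, and a site-reporting trigger and a laboratory tabulation may properly use different thresholds. Much of this stands. The SAP does not need to be told to choose a definition, and the definition sentences differ only in the transaminase reference; treatment emergence and direct bilirubin come from the protocol's reporting bullets. What remains is an unexplained difference under one name, in a study where both versions feed the safety output.

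Four stronger inferences are tempting, and the documents do not support them.

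- That protocol-defined liver cases are lost. They are not: sites report them as events of special interest.
- That a stable high ALT is itself counted as a case. It is not: a complete case also needs a new bilirubin rise above 2x ULN or jaundice, with other causes excluded.
- That the report will show two conflicting Hy's Law counts. No separate count is promised in the special-interest summary. "The most appropriate diagnosis or (if a diagnosis cannot be established) the abnormal laboratory values should be recorded", Protocol 5.3.5.2 tells sites to "record only liver failure or hepatitis rather than jaundice, asterixis, and elevated transaminases", terms are coded to MedDRA, and the same list contains Grade 3 or higher "hepatitis or elevations in AST or ALT". Site-reported and laboratory-derived cases could also differ under identical thresholds, because excluding other causes takes judgement.
- That patients going from normal to Grade 3 or higher disappear. SAP 5.6.2 compares grade with baseline without restriction and SAP 5.6.3 identifies Grade 3 and 4 values, so they may be visible elsewhere.

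It is also fair to say that the primary analysis is done (Protocol 1.2.2.2, cutoff 18 February 2022), which limits what a change can now achieve.

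**Conclusion.** The mismatch is real and minor. Inside the entry limits the two transaminase limbs agree for every peak only at a baseline of 1x ULN, and the window of disagreement widens to >3 to 15x ULN at the 5x limit. A patient who enters above 3x ULN meets the SAP transaminase limb with no change on treatment. The missing normal-baseline row is a lesser point about one described table.

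This rests on reading both definitions as written and on baselines within the entry limits. The documents give no baseline ALT/AST distribution, so the number of patients affected cannot be computed and may be small. No endpoint, test or estimand changes. The documents do not show which threshold is right, and this point takes no position on that.

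**What to change.** Protocol 5.3.5.7 and SAP 5.6.3 must be reconciled. Nothing here presumes which threshold should stand or changes a reporting or treatment rule; whoever reconciles them should bear in mind that Protocol 5.2.3 and Table 1 in 5.1.3.3 rely on the protocol version.

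In SAP 5.6.3, for outputs still to come:

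1. Note that the laboratory definition differs from Protocol 5.3.5.7, and count cases by arm under each definition, labelled.
2. Use values after the first dose, and flag and count separately the cases whose baseline ALT or AST was already above 3x ULN.
3. Extend the shift table to baseline Grades 0, 1 and 2.

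The cost is a few sentences, the additional counts and one table row. ALT, AST, and total and direct bilirubin are already collected (Protocol 4.5.7), and SAP 5.1 already defines baseline. The jaundice limb and the exclusion of other causes draw on clinical records already kept.

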5.6.4 Exploratory Safety Analyses

The exploratory safety objective for this study is to evaluate the tolerability of GDC-9545 compared with physician's choice of endocrine monotherapy based on the following endpoints:

- Presence, frequency of occurrence, severity, and/or degree of interference with daily function of selected symptomatic treatment toxicities, as assessed through use of the NCI Patient-Reported Outcomes Common Terminology Criteria for Adverse Events (PRO-CTCAE).
- Overall tolerability (i.e., bother experienced due to side effects of treatment), as assessed through the General Population, Question 5 (GP5) item from the Functional Assessment of Cancer Therapy-General (FACT-G) questionnaire.
- Change from baseline in symptomatic treatment toxicities and overall tolerability/side-effect burden, as assessed through use of the PRO-CTCAE and the GP5 item, respectively.

In this study PRO-CTCAE is composed of seven adverse events selected from the NCI item bank; {diarrhea, nausea, vomiting, decreased appetite, fatigue, mouth sores, and rash}. The population to be used for the analysis of PRO-CTCAE is the safety evaluable population.

PRO-CTCAE analyses will be descriptive, with a focus on characterizing the pattern of symptomatic treatment toxicities over the course of the study. The numeric scores indicate an ordinal, rather than continuous outcome; therefore, analysis will focus on frequency counts and percentages. The number and percentage of patients reporting each symptom and the change from baseline by category (frequency of occurrence, severity, or

interference) will be summarized at each assessment time point by treatment arm. The worst post-baseline score will be summarized per treatment group, for each individual attribute and AE, and shift tables will be provided per treatment group. For items rated on a 5-point Likert scale, the maximum post-baseline score and change from baseline will be summarized by treatment arm.

Results from these exploratory analyses will be presented separately from the safety analyses. PRO-CTCAE data will be analyzed at the item level. Graphical representation of PRO-CTCAE data over time will also be provided. PRO-CTCAE data will be summarized over time. These analyses will also apply to the GP5 overall treatment burden item. A descriptive analysis of absolute scores and the proportion of patients selecting each response option at each assessment time point by treatment arm will be reported for the FACT-G single-item GP5. The proportion of missing data at each assessment time point will also be summarized to facilitate interpretation of data.

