- ^b Patients who discontinue study treatment will return to the clinic for a treatment discontinuation visit 30 (+3) days after their final dose of study treatment (unless final dose resulted in a dose delay prior to decision to discontinue). For the control arm, the upper limit of the visit window will be dependent upon maximum dosing delay as permitted per local guidelines. The visit at which response assessment shows progressive disease may be used as the treatment discontinuation visit if it falls within 28 (+3) days after the patient's final dose of study treatment.
- ^c Patients should receive their first dose of study treatment on the day of randomization, if possible, but no later than 3 business days after randomization.
- ^d Patients who experience disease progression will discontinue treatment (except in the case of isolated brain metastases as outlined in Section 4.4.3) and enter a follow-up period during which survival and new anti-cancer therapy information will be collected every 6 months or more frequently until death (unless the patient withdraws consent or the Sponsor terminates the study).
- ^e Informed consent must be documented before any study-specific screening procedure is performed and may be obtained up to 6 weeks before initiation of study treatment. Patients who do not meet the criteria for participation in this study (screen failure) must re-sign the consent form prior to re-screening.
- ^f Vital signs include respiratory rate, pulse rate, and systolic and diastolic blood pressure while the patient is in a seated position, and temperature.
- ^g Complete physical examination includes evaluation of the head eyes, ears, nose, and throat, and the cardiovascular, dermatologic, musculoskeletal, respiratory, gastrointestinal, genitourinary, and neurologic systems.
- ^h Perform a limited, symptom-directed examination at specified postbaseline timepoints and as clinically indicated at other timepoints.
- ⁱ 12-lead ECG recordings will be obtained during screening; on Day 1 of Cycles 1, 2, and 4; on Day 1 of every four cycles thereafter (i.e., Cycles 8, 12, 16, etc.); at the treatment discontinuation visit; and as clinically indicated at other timepoints. Patients should be resting in a supine position for at least 10 minutes prior to ECG recording (see Section 4.5.8).
- ^j LVEF to be measured using multiple-gated acquisition scan or echocardiogram.

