- ^s Tumor assessments should be performed as per instructions in Section 4.5.6. All screening tumor assessments (unless otherwise specified) should be completed within 28 days prior to randomization. Brain CT/MRI is required at screening only if clinical indicated or when a patient had previously treated brain lesions. At subsequent tumor assessment time points, brain scans should be acquired if disease was present at baseline or if clinically indicated. Response must be assessed by the investigator according to RECIST v1.1 (see Appendix 4). Patients who discontinue study treatment for any reason other than disease progression or death should continue to undergo tumor assessments every 8 weeks (± 7 days) from randomization for the first 18 months, then every 12 weeks (± 7 days) thereafter, as per instructions.
- ^t Bone scan to be performed at screening. Evaluable bone lesions should be assessed as per RECIST v1.1 (see Appendix 4) every 8 weeks (± 7 days) from randomization for the first 18 months, then every 12 weeks (± 7 days) thereafter. Bone scans are to be repeated every 24 weeks (± 7 days) or as clinically indicated, as per instructions in Section 4.5.6.

- ^u PRO assessments (PRO-CTCAE [Appendix 8], GP5 [Appendix 10], EORTC QLQ-C30 [Appendix 5], BPI-SF "worst pain" item [Appendix 7], EQ-5D-5L [Appendix 9], and EORTC QLQ-BR23 [Appendix 6]) will be completed before the patient receives any information on disease status, prior to the performance of non-PRO assessments, and prior to the administration of study treatment. Questionnaires are to be administered on Day 1 of Cycles 1, 2, and 3, Day 1 of every other cycle thereafter (i.e., Cycles 5, 7, 9, etc.), and at the treatment discontinuation visit. The QLQ-BR23 is to be given immediately after the QLQ-C30; male patients may be exempt from some of the questions included in the QLQ-BR23 module. For patients who discontinue study treatment for reasons other than disease progression, PRO assessments will continue to be administered according to the schedule of tumor assessments (i.e., every 8 weeks [\pm 7 days] from randomization for the first 18 months, then every 12 weeks [\pm 7 days] thereafter).

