5.1 GENERAL CONSIDERATION

All efficacy analyses will be performed on the full analysis set population, unless otherwise specified. All safety analyses will be performed in the safety-evaluable population, unless otherwise specified.

Analyses of demographics and other baseline information will be based on full analysis set population. The baseline value of any variable will be defined as the last available data point prior to the first administration of study drug.

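### SAP 5.6.4 sets no end to the window for the worst PRO-CTCAE and GP5 score, so scores given under new anti-cancer therapy or long after the last dose can be reported as tolerability of the study treatment

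*SAP*

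**What the plan says.** **Analysis.** SAP 5.6.4 describes PRO-CTCAE as "characterizing the pattern of symptomatic treatment toxicities over the course of the study". For the summary measure it says "The worst post-baseline score will be summarized per treatment group, for each individual attribute and AE", with shift tables, and for the 5-point items "the maximum post-baseline score and change from baseline will be summarized by treatment arm". It then adds: "These analyses will also apply to the GP5 overall treatment burden item". The start of the window is fixed in SAP 5.1: "The baseline value of any variable will be defined as the last available data point prior to the first administration of study drug". No end of window is given, and there is no rule for scores given after another cancer therapy has started. SAP 5.6 groups the safety population by treatment received.

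**Collection.** Protocol Appendix 1, footnote u: "Questionnaires are to be administered on Day 1 of Cycles 1, 2, and 3, Day 1 of every other cycle thereafter", and again at the treatment discontinuation visit. Footnote b places that as a "treatment discontinuation visit 30 (+3) days after their final dose of study treatment". It lets the visit that shows progression serve instead if it falls within 28 (+3) days of the final dose, and in the control arm the upper limit of the window follows local rules on dosing delay. For patients who stop for reasons other than progression, footnote u says "PRO assessments will continue to be administered according to the schedule of tumor assessments", that is every 8 weeks for 18 months and every 12 weeks after that. Protocol 4.5.6.2 keeps that schedule running in patients who have started another cancer therapy.

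**The concern.** The stated purpose of SAP 5.6.4 is to compare the tolerability of GDC-9545 with that of endocrine monotherapy. A worst score is a maximum, so each further assessment can raise it and none can lower it. If assessments under a different treatment are eligible, a single bad week on next-line therapy can fix a patient's worst score, and the table will show it under the study treatment. GP5 is the most exposed item. It asks how much the side effects of treatment have bothered the patient over the past 7 days and does not name the treatment, so a patient on a new regimen would naturally answer for that regimen.

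At stake is the meaning of one descriptive table per instrument. No primary, secondary or formal safety analysis uses it.

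**Working it through.** The plan states no figure for this analysis, so there is none to reproduce. The check lays the visit calendar over the analysis text and then asks what extra assessments do to a maximum.

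**1. Is off-treatment data eligible?** Start of window: last value before first dose (SAP 5.1). End of window: none (SAP 5.6.4). PRO-CTCAE and GP5 are both collected after the last dose (Appendix 1, footnotes b and u). They are eligible because nothing excludes them; the SAP does not expressly include them.

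**2. The discontinuation visit.** The visit is at day 30 to 33 after the final dose, and both instruments have a 7-day recall (Protocol 4.5.9.2). The recalled period therefore lies between day 30 − 7 = 23 and day 33, with no day on daily GDC-9545. This does not hold when the progression visit is used instead. After progression, Protocol 4.4.3 bars other cancer therapy only until progression is documented and study treatment has stopped, so next-line therapy by day 30 is allowed. Its frequency is not stated.

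**3. Weight of that one visit.** On-treatment assessments after baseline fall on days 29, 57, 113, 169, 225 and so on (Cycles 2, 3, 5, 7, 9).
- Treated for 5.5 months (5.5 × 30.44 = 167 days): 3 on treatment plus 1 at discontinuation, so 1/4 = 25% of post-baseline assessments.
- Treated for 8.5 months (259 days): 5 plus 1, so 1/6 = 17%.

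**4. Stops without progression.** These patients stay on the 8-weekly schedule from randomisation until progression. With the last dose at day 56, 112 or 168, up to 8, 7 or 6 further assessments fall after the discontinuation visit and within 18 months, the first of them 56 days after the last dose. All are eligible for the worst score, whether or not new therapy has started. After progression, by contrast, neither instrument is given beyond the discontinuation visit (footnotes u and v).

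**5. Effect on a maximum.** Let p be the chance of a high score at each of k on-treatment visits and q the chance at one later visit, all independent. The share with a high worst score is 1 − (1 − p)^k without the later visit and 1 − (1 − p)^k (1 − q) with it. Take k = 3 and p = 5% (assumed):
- on treatment only: 1 − 0.95³ = 14.3%
- plus one visit at q = 5%, 10%, 15%, 30%: 18.5%, 22.8%, 27.1%, 40.0%

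Even at q = p the share rises, because there is one more draw.

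**6. Does it favour one arm?** A simulation used SAP Table 2 accrual, a month-18 cutoff, exponential PFS with medians 5.5 and 8.5 months, progression detected at 8-weekly scans, and one discontinuation assessment after each progression. The on-treatment item distribution was the same in both arms (0.50/0.25/0.15/0.08/0.02, assumed), with scores independent between visits. About 57% of control and 43% of GDC-9545 patients reach a discontinuation visit by the cutoff. Share with a worst score in the top two categories:

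| Rule | Control | GDC-9545 | GDC-9545 minus control |
|---|---|---|---|
| On treatment only | 33.4% | 36.0% | 2.6 points |
| Plus discontinuation visit, same scores | 37.5% | 39.0% | 1.5 |
| Plus discontinuation visit, worse scores (0.35/0.25/0.22/0.13/0.05) | 40.6% | 41.4% | 0.8 |

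True tolerability is equal by construction. The 2.6-point gap in the first row arises only because longer treatment gives more assessments. The extra visit raises control by more (37.5 − 33.4 = 4.1 points against 39.0 − 36.0 = 3.0), yet control does not come out worse in any row. The rises also depend on independence: with a within-patient correlation of 0.7 and the same score distribution, they fall to about 1.5 points in control and 1.1 in GDC-9545. The share of discontinued patients whose worst score comes only from that visit falls from about 17% to about 10%.

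**The case against.** **A reader might infer that the rule makes the control arm look worse tolerated.** The documents do not support this. More control patients are expected to reach a discontinuation visit, but in the simulation that only narrows a gap which longer treatment had opened against GDC-9545. The result rests on assumed item distributions and an assumed correlation, and the documents give no frequency of next-line therapy by day 30. The objection stands: no direction can be claimed.

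**A day-30 score is arguably still within the treatment period.** Safety follow-up and adverse event reporting run to 30 days after the final dose (Protocol 3.1.1, 5.3.1). Fulvestrant is described as a monthly injection (Protocol 1.2.1), so day 30 is about the end of a dosing interval. A cut-off tied to the 7-day recall could drop real fulvestrant effects in control alone. This stands, and it is why the fix does not close the window at the last dose.

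**Not every discontinuation visit is a month off drug.** The progression visit may take its place, so recall may fall on treatment. This also stands.

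**The long tail may be thin.** It affects only patients who stop without progression. Protocol 1.2.2.2 reports adverse event withdrawals of 2 (1.3%) and 3 (2%); other stops without progression are not given. This limits the size and leaves the gap in the rule.

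**The stakes are low.** The same data are shown by timepoint and graphed, and SAP 5.6.4 presents them apart from the safety analyses. That is true, but the by-timepoint tables do not repair a worst-score table that mixes treatments.

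**Conclusion.** The point holds in limited form. As written, SAP 5.6.4 lets scores that reflect next-line therapy, or that were given long after the last dose, set the worst PRO-CTCAE or GP5 score attributed to the treatment received. This follows from the text without any assumption about rates.

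The size is not established. One added assessment is 25% of the post-baseline assessments for a patient treated 5.5 months and 17% at 8.5 months, and a stop without progression can add up to eight more. What this does to the table depends on score distributions, within-patient correlation and the frequency of new therapy, none of which the documents give. The percentages in the working are illustrations.

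Two further readings go too far. The misattribution is not to the randomised arm, since grouping is by treatment received. Nor does the SAP close all other patient-reported data at discontinuation: SAP 5.4.6 does so for the five time-to-deterioration endpoints only, and the QLQ-C30 and QLQ-BR23 summaries in SAP 5.5 carry no such limit.

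**What to change.** In SAP 5.6.4, derive the worst or maximum post-baseline score and the shift tables, for PRO-CTCAE and GP5 alike, only from assessments made before any new anti-cancer therapy and no later than the discontinuation visit. This is consistent with the protocol's 30-day safety window. Tabulate later scores, and scores after new therapy, separately as off-treatment data. Label the discontinuation visit as its own timepoint in the by-timepoint summaries. A sensitivity table limited to assessments up to the last dose can be added, to show how much the discontinuation visit contributes.

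The cost is one sentence and a date filter: dosing dates, assessment dates and new anti-cancer therapy are already collected. The downside is that a few collected scores leave the worst-score table, and a patient whose only post-baseline score follows new therapy contributes none. The number of such patients should be given in a footnote to the table.
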